### Primary Objective 2.3.1:

- Women in Cohort 1 will comprise the analysis sample. A binary indicator, “optimal adherence” will be created, as defined above as TFV-DP levels in DBS meeting or exceeding the threshold determined in the PK Component as corresponding to protective levels of PrEP (24). At each visit that TFV-DP levels are obtained (see [Appendix IIA](#)), the proportion of women with optimal adherence will be calculated based on their TFV-DP levels at each visit. The proportion of visits with optimal adherence in the pregnancy vs. postpartum periods will be calculated and compared.
- Exploratory analyses identifying baseline and time-varying predictors of optimal adherence will be conducted with multivariable regression models using generalized estimating equations with a logistic link (to account for repeated measures across time for each participant).
- Adherence (as measured in TFV-DP levels) will also be summarized as a continuous outcome (median, IQR and mean [SD]) at each time point noted above when drug levels are measured, and “average” adherence across pregnancy and postpartum periods, will be calculated, using generalized estimating equations. We will focus on periods during which the participant has formally elected to be on PrEP. If a woman elects to formally stop PrEP (by notifying study personnel), periods of being formally off study drug will not be considered in adherence calculations.
- Other approaches to summarizing the adherence outcome will be considered. This includes an ordinal variable with categories corresponding to different dosing levels. For this type of outcome, at each visit that drug levels are measured in DBS, descriptive analyses will summarize the proportion of women in each adherence category, refer to categories discussed in [Section 9.1.6](#).

- Baseline characteristics, and patterns of adherence and duration on PrEP will be summarized separately for women in Cohort 2 who later decide to initiate PrEP using the approaches outlined above.
- The following additional descriptive statistics will be calculated: The proportion of women a) with at least one visit with TFV-DP levels corresponding to optimal adherence, b) who had TFV-DP levels corresponding to optimal adherence at all visits, c) who had no detectable TFV-DP levels at any visit.

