2.2.2 Hypotheses for the PrEP Comparison Component

1. At least 75% of women who opt to initiate PrEP will achieve a high level of adherence throughout pregnancy, as measured by optimal TFV-DP concentrations in DBS specimens.
2. The rate of maternal and infant adverse events (including adverse pregnancy outcomes) will be higher among mother-infant pairs in which the mother initiates PrEP during pregnancy or postpartum than in pairs in which the mother declines PrEP.

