- **Adherence Set:** All maternal participants on PrEP, including those in Cohort 1 and those in Cohort 2 who later decide to formally initiate PrEP. All visits/periods where maternal participants are actively prescribed PrEP.
- **Maternal Safety Set:** All maternal participants in Cohort 1 or Cohort 2, starting at enrollment
- **Infant Safety Set:** All liveborn infants in Cohort 1 or Cohort 2, starting at birth

5 General Considerations – PrEP Comparison Component

The primary analyses to address the primary objectives of the PK Component and the PrEP Comparison Component are outlined below. For a more detailed description of the analyses to be conducted, please refer to the Analysis Implementation Plan (AIP).

Categorical variables will be summarized as N (%), with corresponding 95% confidence intervals where applicable. Continuous variables will be summarized with means and standard deviations, medians and IQR (Q1, Q3), as well as min, max.

Descriptive summaries:

PK Component: We will summarize and compare demographic and clinical characteristics at enrollment between maternal PK Component Group 1 (enrolled in pregnancy) and maternal PK

Component Group 2 (enrolled postpartum). We will use Fisher's exact test to estimate differences in proportions and t tests or Wilcoxon rank-sum tests (as appropriate) for continuous measures.

PrEP Comparison Component: Entry demographic, pregnancy, pregnancy history, psychosocial, sexual behavior and partner characteristics of women in Cohort 1 and Cohort 2 will be summarized and compared using chi square tests (or Fishers exact test as appropriate) for discrete variables and t-tests or Wilcoxon tests for continuous variables.

6 Estimands and Estimation

6.1 Primary Estimand PK Component:

Primary Objective 1: To determine the concentration of tenofovir diphosphate (TFV-DP) associated with adequate adherence to FTC/TDF among women observed ingesting daily oral PrEP during pregnancy and postpartum.	
Estimand description	Maternal Steady state TFV-DP concentrations at Week 12
Treatment	1. Daily oral PrEP (200 mg FTC/ 300 mg TDF) during pregnancy and/or postpartum administered through direct observation.
Target population	Analysis set

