6.3 Primary Estimand(s) - PrEP Comparison Component

6.3.1 First Primary Estimand

Primary Objective 1: To characterize PrEP adherence among HIV-uninfected young women during pregnancy and for twenty-six weeks postpartum, when provided with enhanced adherence support through mobile technology and counseling based on observed drug levels.	
Estimand description	The probability that pregnant and postpartum HIV-uninfected women will have optimal adherence to daily oral PrEP 1) at defined timepoints; 2) during pregnancy and postpartum (through twenty-six weeks) as measured in TFV-DP concentration levels in dried blood spots during periods when women are formally prescribed PrEP

Treatment	
 1. Daily oral PrEP (200 mg FTC/ 300 mg TDF) during pregnancy and/or postpartum. 2. Enhanced adherence support, including SMS messaging and feedback of drug levels with tailored counseling. 3. Behavioral HIV risk reduction package
Target population	Analysis set
Women who are pregnant and HIV-uninfected, 16-24 years of age, with a confirmed singleton pregnancy of 32 weeks' gestation or less and who have access to a mobile phone, are able to receive and read SMS messages, and express willingness to take PrEP anytime between pregnancy and 26 weeks postpartum	Adherence set: Women initiating PrEP
Variable(s)	Outcome measure(s)
TFV-DP drug concentration level	
 1. TFV-DP drug concentration level from Dried Blood Spots (DBS) measured in pregnancy at 4, 8, 12, 24, 36 week study visits, Labor and Delivery, and postpartum at 6, 14, and 26 week study visits during the periods that participants are receiving PrEP. A binary indicator, "optimal adherence" will be defined as TFV-DP levels meeting or exceeding the threshold of consistent dosing of PrEP ("Green Zone") determined in the PK Component (Appendix Tables 1-2). For women who are pregnant the threshold is 600 fmol/punch if on PrEP \leq 6 weeks and 650 fmol/punch if $>$ 6 weeks; for women who are not pregnant the threshold is 700 fmol/punch if on PrEP \leq 6 weeks and 1050 fmol/punch if on PrEP $>$ 6 weeks. 2. Visits with optimal adherence according to TFV-DP level during pregnancy and during postpartum
Handling of intercurrent events	Handling of missing data

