
 • Failure to start PrEP (in Cohort I or Cohort 2/Step 2) (Treatment policy strategy) • Discontinuation of PrEP: Only visits occurring prior to discontinuation of PrEP will be included. (While on treatment strategy) • HIV seroconversion: Only visits occurring up to the later of the date of first positive HIV test or date when PrEP is discontinued will be included. (While on treatment strategy) 	
Missing data could occur in the following situations:
 
 • Missing visit(s) when adherence would have been assessed • Missing drug concentration results due to sample collection or processing issues. 
Visits without adherence data will be excluded. Sensitivity analyses will be conducted imputing "suboptimal adherence" for each missed visit/concentration result

Population-level summary measure	Analysis approach

 1. Probability of optimal adherence according to TFV-DP levels in DBS at defined times during pregnancy and postpartum 2. Probability of optimal adherence while pregnant and up to 26 weeks postpartum 	
 1. At each visit that TFV-DP levels are obtained, the binomial proportion of women with optimal adherence will be calculated bounded by an exact (Clopper-Pearson) 95% confidence interval. 2. The binomial proportion of visits with optimal adherence in pregnancy and postpartum periods during periods when women are

	formally prescribed PrEP will be calculated with exact (Clopper-Pearson) 95% confidence intervals.
--	--

Supplemental Analyses:

- Exploratory longitudinal analyses identifying baseline and time-varying predictors of optimal adherence will be conducted with multivariable regression models which account for repeated measures across time for each participant.
- Adherence (as measured in TFV-DP levels) will also be summarized as a continuous outcome measure (median, IQR and mean [SD]) at each time point noted above when drug levels are measured, and “average” drug concentrations across pregnancy and postpartum periods, will be calculated, using generalized estimating equations as appropriate. Log transformation of this outcome will be considered if the distribution is not normal.

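### Hypothesis 1 covers all women who start PrEP, throughout pregnancy, but the adherence estimates cover only time on a formal prescription, so they can look more favourable to the 75% claim than the result among all initiators.

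*SAP*

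**What the plan says.** Protocol 1.5 and SAP 2.2.2 give the same first hypothesis: "At least 75% of women who opt to initiate PrEP will achieve a high level of adherence throughout pregnancy", measured by TFV-DP in dried blood spots.

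The adherence analyses are limited to time on prescription at each level:

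- **Analysis set** (SAP section 4, Adherence Set): "All visits/periods where maternal participants are actively prescribed PrEP".
- **Estimand** (SAP 6.3.1): adherence is measured "during periods when women are formally prescribed PrEP".
- **Discontinuation** (SAP 6.3.1, while-on-treatment strategy): "Only visits occurring prior to discontinuation of PrEP will be included".
- **Protocol 9.2.6, Primary Objective 2.3.1**: after a formal stop, "periods of being formally off study drug will not be considered in adherence calculations".
- **Missing data** (SAP 6.3.1): "Visits without adherence data will be excluded". The sensitivity analysis imputes suboptimal adherence for missed visits or results only, not for visits after a formal stop.
- **Woman-level summary** (SAP 6.3.1, supplemental analyses): the proportion of women optimal at all visits is also confined to prescribed time.

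Failure to start is handled differently, under a "Treatment policy strategy", so those women stay in. The supplemental analyses also report the proportion of initiators who formally stopped, their reasons, a comparison of stoppers with continuers, and the share of follow-up time on PrEP. SAP section 7 lists discontinuation and restart in the final report.

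**The concern.** The hypothesis makes a claim about women: of those who start, how many keep high levels through pregnancy. The planned estimates answer a different question: how good the levels are while a woman is still formally on the drug. Both questions are legitimate, but the second cannot be read as an answer to the first when some women stop before delivery.

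The documents themselves link stopping with adherence. Protocol 3.2.1 places early discontinuation in the non-adherent interview group, and protocol 3.2 says switching on and off PrEP is monitored among the feasibility and adherence outcomes. Within the estimand, a woman who never takes a tablet counts against adherence, while one who tells staff she has stopped drops out of later denominators.

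At stake is how a headline result on a primary objective is interpreted. A figure of 75% or more among women still prescribed PrEP could be taken as support for Hypothesis 1 when the proportion among all initiators is lower. The plan does not say which estimate is to be read against the hypothesis.

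**Working it through.** **Step 1. The plan's own precision figure.** Protocol 9.2.4, Table 8, gives 68-81% for 75% adherent with 200 women in Cohort 1. The exact Clopper-Pearson interval for 150/200 is 68.4% to 80.8%, which rounds to 68-81%. The width is 12.4 points, or 13 from the rounded limits. The figure reproduces. It treats all 200 women as the denominator.

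**Step 2. One visit, all initiators in the denominator.** Inputs: 200 initiators (protocol 9.2.4); 75% optimal among those still on PrEP (the hypothesised value); a fraction *s* who have formally stopped by that visit. The documents give no value for *s*, so 5% to 30% is assumed. Women off PrEP are counted as not optimal:

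proportion among all initiators = 0.75 × (1 − s)

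| s (assumed) | still on PrEP | optimal | among all 200 | 95% Clopper-Pearson |
|---|---|---|---|---|
| 5% | 190 | 142 | 71.0% | 64.2-77.2% |
| 10% | 180 | 135 | 67.5% | 60.5-73.9% |
| 20% | 160 | 120 | 60.0% | 52.9-66.8% |
| 30% | 140 | 105 | 52.5% | 45.3-59.6% |

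(For 5%, 0.75 × 190 = 142.5 is taken as 142.) At 10% and above the upper limit lies below 75%; at 5% it does not.

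**Step 3. What the on-PrEP figure would have to be.** For 75% of all initiators to be optimal at that visit, the proportion among those still on PrEP must be 0.75 / (1 − s): 0.75/0.95 = 78.9%, 0.75/0.90 = 83.3%, 0.75/0.80 = 93.8%. Above s = 25% the target cannot be reached, although the on-PrEP estimate could still read 75% or more.

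**Step 4. Can a reader rebuild the woman-level figure from what is reported?** Let A be the proportion of women optimal at all prescribed visits. Those who were optimal and then stopped are inside A. The proportion optimal throughout and never stopped therefore lies between A − s (every stopper was optimal beforehand) and the smaller of A and 1 − s. With A = 75% and s = 20%, that is 55% to 75%. Reporting A and s separately leaves this range open; the joint count is needed. The planned statistic is also not limited to pregnancy visits.

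**Step 5. Limit of the illustration.** Step 2 concerns one visit. Being optimal at every visit is a stricter measure even if nobody stops: with 75% at each of Weeks 4, 8 and 12, it lies between 0.75³ = 42% (visits independent) and 75% (perfectly correlated). The Step 2 shortfalls must not be carried over to the woman-level measure.

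**The case against.** The strongest defence is that adherence while prescribed and persistence on PrEP are different quantities, and the plan separates them openly and consistently across protocol and SAP. The primary objective is to characterise adherence. The SAP estimates proportions with confidence intervals and tests nothing against 75%. Stopping, its reasons and time on PrEP appear beside the adherence results. All of this stands, and it is why the declared estimand should stay.

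Three stronger readings are tempting and are not supported:

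- *That the 75% claim is assessed only in women who stay on.* This is true of each visit's denominator, but women who later stop contribute their visits before stopping. Non-starters stay in, and so do women who stop taking tablets without telling staff.
- *That the trial will declare the hypothesis met.* There is no decision rule; the risk lies in interpretation.
- *That every stop is an adherence failure.* Protocol 8.3 and Appendices IV and V also require stops, for confirmed HIV infection, drug-related laboratory abnormalities and reduced creatinine clearance. A supplementary analysis must show these separately.

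What the defence does not answer is that no listed analysis has the population and period of Hypothesis 1, and that separate reporting of stopping does not supply one (Step 4).

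**Conclusion.** The mismatch is real and moderate in importance. Hypothesis 1 concerns all initiators throughout pregnancy; every planned adherence estimate conditions on prescribed time. Where women stop, the planned figures can look more favourable to the 75% claim than the result among all initiators.

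The size depends wholly on the stopping rate, which the documents do not give. At a single visit, with 75% optimal among those on PrEP and stoppers counted as not optimal, the gap is 4 points at 5% stopping (75 − 71), 7.5 points at 10% and 15 points at 20%. If few women stop before delivery, it is negligible. A reader might infer concealment or a biased primary estimand; the documents show neither, because the restriction is stated and the stopping proportion is reported.

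**What to change.** Keep the while-on-PrEP estimand. Add one supplementary analysis to SAP 6.3.1 among all Cohort 1 women, that is, those who opted to start at entry. Women from Cohort 2 who start later may have no pregnancy visits on PrEP and should be left out of it.

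1. **Per visit.** At each pregnancy visit, use all women still pregnant and in follow-up as the denominator and count visits while formally off PrEP as not optimal.
2. **Per woman.** Report the proportion optimal at every pregnancy visit, with a formal stop before delivery counted as not achieved. State which visits count as pregnancy visits.
3. **Intervals and missing data.** Use Clopper-Pearson 95% intervals and the existing rule for missed visits, including its sensitivity analysis.
4. **Reasons.** Show voluntary and protocol-required stops separately, or add a sensitivity analysis excluding the latter.
5. **Reading.** State that the woman-level measure is the one read against Hypothesis 1.

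The alternative is to restate Hypothesis 1, in protocol and SAP, as adherence while formally prescribed PrEP.

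Cost: one extra table. Under protocol 6.2.3.1 the decision to stop is recorded on an eCRF, and Cohort 1 women who stop stay on their visit schedule apart from drug-level feedback counselling, so no new data are needed. Label: free improvement.

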2.3 Primary and Secondary Study Objectives

2.3.1 Primary Study Objective for the PK Component

- To determine the concentration of tenofovir diphosphate (TFV-DP) associated with adequate adherence to FTC/TDF among women observed ingesting daily oral PrEP during pregnancy and postpartum.

2.3.2 Secondary Study Objective for the PK Component

- To compare TFV-DP concentrations observed in pregnant and postpartum women.

2.3.3 Primary Study Objectives for PrEP Comparison Component

This Primary SAP addresses the following primary objectives in the study protocol. Other study objectives in the protocol will be addressed in subsequent analysis plans.

- To characterize PrEP adherence among HIV-uninfected young women during pregnancy and for twenty-six weeks postpartum, when provided with enhanced adherence support through mobile technology and counseling based on observed drug levels.
- To assess the safety of FTC/TDF for PrEP during pregnancy and postpartum by comparing pregnancy outcomes and maternal and infant safety between PrEP-exposed and PrEP unexposed groups.

The Primary SAP includes objectives, estimands and outcome measures to be addressed in the primary analysis report for the PrEP Comparison Component. The analysis or monitoring reports prepared by the SDMC for IMPAACT 2009 will include monthly monitoring reports, annual and ad hoc SMC reports, and a final report to be prepared after all participants have completed their last follow up visit.

2.4 Overview of Sample Size Considerations

2.4.1 PK Component:

The PK Component will enroll a total of 40 women (20 in Group 1 and 20 in Group 2) to achieve a sample size of at least 30 evaluable participants, accounting for attrition.

2.4.2 PrEP Comparison Component:

The PrEP Comparison Component will enroll a total of 350 (233 in Cohort 1 and 117 in Cohort 2) women over a 12-month period. Women will be followed through 26 weeks postpartum. Sample size and power calculations assume a final analysis sample of 300 women (200 in Cohort 1 and 100 in Cohort 2) with follow-up through 26 weeks postpartum. The primary reason for the 2:1 enrollment into the two cohorts was to balance the need for a “No PrEP” comparison group (to provide the background rates for safety outcome measures) with the need for a large enough PrEP group to examine outcomes that would be restricted to women in that group and the periods when they were prescribed PrEP (Adherence). To achieve this sample size at the analysis phase, this study will enroll approximately 350 women to accommodate a decrease of an estimated 15% due to maternal attrition. This is an abbreviated summary of details in the study protocol; refer to the IMPAACT 2009 protocol for additional details.

2.5 Overview of Formal Interim Monitoring

PK Component and PrEP Comparison Component: The Clinical Monitoring Committee (CMC) on behalf of the Protocol Team will closely monitor study progress, safety, quality of study conduct, and participant accrual and retention based on reports that will be generated at least

monthly by the SDMC. In addition, an independent IMPAACT Study Monitoring Committee (SMC) will review this study regularly, following policies described in the IMPAACT Manual of Procedures. The composition of the SMC will include the SMC Chair; IMPAACT Chair or Vice-Chair; IMPAACT HIV Treatment Scientific Committee representative; representatives of the IMPAACT Operations Center and Statistical and Data Management Center; and representatives of NIAID and NICHD.

SMC reviews will occur at least annually and on a more frequent or ad hoc basis if any safety issues or concerns arise. Ad hoc reviews may also be triggered per the safety monitoring guidelines specified below. Based on any of its reviews, the SMC may recommend that the study proceed as currently designed, proceed with design modifications, or be discontinued. The SMC may also provide operational recommendations to help address any study implementation challenges that may be identified during their reviews.

The SMC will monitor study progress, quality of study conduct, and participant safety. The SMC will generally review the same types of data reports as the Protocol Team and CMC. For ad hoc or triggered safety reviews, more limited data may be reviewed, focusing on the events that triggered the reviews.

PrEP Comparison Component Only: Adverse events in both groups and the proportion of women with Week 12 TFV-DP drug levels below the limit of quantification in Cohort 1 (as well as decisions to initiate PrEP after study entry among women in Cohort 2) will be monitored and summaries prepared at regular intervals for review by the SMC. The following events will trigger a SMC review.

- Monitoring the proportion of women in Cohort 1 without quantifiable levels of TFV-DP at Week 12 (excluding women who have decided to stop PrEP):
 - At any site, if this proportion at Week 12 is greater than 40% after 15 maternal participants in Cohort 1 have completed that study visit and have TFV-DP specimen data available for that visit, the CMC will review the data and consult with site investigators, and make a recommendation to the SMC regarding the need for remedial actions or discontinuation of enrollment at the site. The SMC will convene to consider the CMC's recommendation.
- Monitoring participant safety outcomes (for women or infants in Cohort 1 and Cohort 2, Step 2). *Ad hoc* SMC reviews will be convened:
 - If the proportion of women experiencing Grade 3 or higher adverse events is greater than 15%, after 50 women have been enrolled
 - If the rate of adverse pregnancy outcomes is greater than 20%, after 25% of pregnancies have been completed.
 - If the proportion of livebirth infants experiencing Grade 3 or higher adverse events is greater than 15%, after 50 completed pregnancies resulting in live births.

3 Outcome Measures

